2 TRIAL DESIGN

This is a UK, multicentre, one year, assessor-blind, randomised controlled trial assessing systemic treatments in adults with moderate to severe eczema. Three mechanistic classes of drugs are being tested against a control (ciclosporin). Further treatments and arms may be added in future amendments.

Participants will be randomised in a 1:1:1:1 ratio. **During the first stage of the trial (months 1-6)**, **follow up will be face to face at 1, 3 and 6 months** for safety and effectiveness assessment (see Figure 2 for trial flow diagram and Table 1 for schedule of events). There are additional drug-specific safety only visits for some arms as shown in Table 1, Figure 2, and individual flow diagrams in drug specific Appendices 1-4, in line with routine care and national guidance. There is the **option to increase the treatment dose at 3 months for some arms if there has been an inadequate response** following which additional safety only visits may be required (see Table 1 schedule of events, Figure 2 trial flow diagram, and individual flow diagrams in drug specific appendices 1-4). Dose reduction will be permitted at any stage as clinically indicated and according to standard clinical practice. Safety only visits (when no additional effectiveness measure is conducted) can be conducted in the community where deemed appropriate by the investigator (general practice). If participants attend study sites, contact with study staff should be minimised and staff will be trained to not provide additional support to minimise performance bias.

The primary outcome will be assessed at 6 months. Responders, defined as those achieving at least a 50% improvement in the objective EASI score (EASI50) and $a \ge 4$ point reduction in Dermatology Life Quality Index (DLQI) will continue the same therapy for a further 6 months (up to 1 year) if they are tolerating the treatment and are happy to continue (in line with NICE guidance (NICE TA534¹⁷)). Non-responders will switch therapy in a pre-determined way that mirrors real world practice (see Figure 2).

In the second stage of the trial (months 7-12) face to face safety and effectiveness assessments will be at 9 and 12 months. For those participants who have switched therapy there will be an additional telephone/ remote safety only visit (with bloods) at 7 months. Dependent upon

the drug that they switch to, additional safety bloods may be required and there may be the option to increase dose at 9 months (requiring further additional safety bloods, see Figure 2).

The pragmatic trial design mirrors routine care as closely as possible. Due to the different safety monitoring requirements of the trial drugs the number of times safety bloods are taken during the trial differs between arms. Patient reported outcomes will be collected via electronic questionnaires at trial visits using a secure online platform (DrDoctor). Topical treatment will be permitted throughout the trial.

This trial is an assessor-blind design. The primary outcome and assessor-rated secondary outcome will be conducted by an independent trained assessor at site, who is blinded to treatment allocation and not involved in the care of the patient. This may be a dermatologist or dermatology nurse who has received full training in using the instruments.

The electronic version of this document is the latest version. It is responsibility of the individual to ensure any paper material is the current version. Printed material is uncontrolled documentation. BEACON_PROTOCOL_VERSION 2.1_29/01/2025 Page 25 of 110

TABLE 1 SCHEDULE OF EVENTS

Event / form	Screening	Baseline ^A	Week 2 Safety Visit ^B	Week 4 (Month 1)	Week 6 Safety Visit ^c	Week 8 Safety Visit ^c	Week 13 (Month 3)	Week 15 Safety Visit ^D	Week 17 Safety Visit ^D	PRIMARY OUTCOME Week 26 (Month 6)	Week 28 Safety Visit ^E	Week 30 Safety Visit ^F	Week 39 (Month 9)	Week 41 Safety Visit ^G	Week 43 Safety Visit ^G	Week 52 (Month 12) End of Study Visit	Ongoing
Informed Consent	Х																
Registration Form	Х																
Eligibility (confirmation only at baseline)	х	х															
Medical History and	х																
Skin photography (optional)		¥								x							
Randomisation Form (after all		X								~							
baseline data collected)		X															
Status Form				Х			Х			Х			Х			Х	
Physical examination*	X	X		Х			Х			Х			X			Х	
Blood pressure	X	X															
	X	v								V++							
Eczema Area and Severity Index (EASI) BLINDED ASSESSOR		x		x			x			x			x			х	
Investigator Global Assessment (vIGA-AD) BLINDED ASSESSOR		x		х			x			x			х			x	
Patient Orientated Eczema Measure (POEM)		х		х			х			х			х			х	
Peak pruritus numerical rating scale (NRS)		х		х			х			х			х			х	
Eczema control (RECAP)		Х		Х			Х			Х			Х			Х	
Patient global assessment (PtGA)		х		х			х			х			х			х	
Dermatology Life Quality Index (DLQI)		х		х			х			х			х			х	
EQ-5D-5L		Х					Х			Х			Х			Х	
PHQ-9		X								X						X	
GAD-7		X					v			X			v			X	
Adherence check (VAS) &							х			x			x			X	
I olerability		v														v	
Dispense medication		Ŷ					Y			Y			Y			^	
Screening blood tests (+DNA			 				Λ										
for filaggrin status, optional)	X				 												
remote)		Х	х	X+++	Х	X	X	Х	Х	X	Х	Х	X++++	X	Х	Х	
be remote)**			Х	X	Х	X	X	Х	Х	X			X			X	
Safety urinalysis**				X			X			X			X			X	
Safety assessment (can be remote)***												Х					
Methotrexate polyglutamate sample****				х			х			х							
Study medication switch review										X							
Study medication dose							х						х				
Concomitant Mediactions Las							-						-				v
Topical treatments		x		X			x			x							^
Adverse Events Loa		~	 				~										Х
Withdrawal Form			1														Х

The electronic version of this document is the latest version. It is responsibility of the individual to ensure any paper material is the current version. Printed material is uncontrolled documentation. BEACON_PROTOCOL_VERSION 2.1_29/01/2025 Page 26 of 110

BEACON

* Physical examination (according to routine clinical care) required at screening and baseline, extent of physical exam during follow up as deemed appropriate by investigator

** Only required for those on ciclosporin

*** Only for those who switched treatment at 6 months

- ****Only required for those on methotrexate
- + Women of childbearing potential only. Urine test

** Repeat pregnancy test at 6 months for patients changing treatment from dupilumab or abrocitinib to methotrexate

*** Not required for those on dupilumab from the start (week 39 blood tests required for those who switch to dupilumab)

++++ Not required for those on dupilumab or abrocitinib from the start (week 39 blood tests required for those who switch to dupilumab)

A: Baseline safety bloods for all treatments, at investigator discretion based upon timing of screening bloods. Baseline safety blood pressure check if randomised to ciclosporin only.

B: Week 2 Safety bloods and safety blood pressure check if randomised to ciclosporin, week 2 safety bloods if randomised to methotrexate

C: Week 6 & 8 Safety bloods and safety blood pressure check if randomised to ciclosporin only

D: Week 15 & 17 Safety bloods and safety blood pressure check if dose increased on ciclosporin, week 15 & 17 safety bloods if dose increased on methotrexate

E: Week 28 Safety bloods only if switched to methotrexate at 6 months

F: Week 30 Safety bloods only if switched to methotrexate at 6 months G: Week 41 & 43 Safety bloods check for patients who switched to methotrexate and dose increased only

OBJECTIVES

3.1 PRIMARY OBJECTIVE

The primary objective of this trial is to determine the effectiveness of systemic treatments for moderate-severe eczema in adults compared with the control systemic treatment ('standard of care') over 6 months (including a pre-specified subgroup analysis examining moderate and severe groups separately).

3.2 SECONDARY OBJECTIVES

- 1. Determine the effectiveness of systemic treatments compared with standard of care over 12 months
- 2. Determine the impact on symptoms, quality of life, daily function and mood of systemic treatments compared with standard of care over 12 months
- 3. Determine the safety / tolerability of systemic treatments compared with standard of care, and adherence to the medications over 12 months
- 4. Determine cost-effectiveness of systemic treatments compared with standard of care over 12 months
- 5. Collect data on which first line therapy optimises treatment continuity over the first year and in the event of a treatment switch, which of the tested pathways optimises treatment outcomes at one year.
- 6. Determine the incidence of AEs of special interest (see section 10.2 for further information) on systemic treatments compared with standard of care over 12 months
- 7. Collect clinical data and samples for use by the scientific community to understand atopic eczema disease biology and treatment response in order to improve outcomes in people with atopic eczema.

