12.2 STATISTICAL ANALYSIS PLAN

A full Statistical Analysis Plan (SAP) will be drafted in accordance with the KCTU Standard Operating Procedures authored and approved by the Trial Steering Committee and Data Monitoring and Ethics Committee.

The Junior Trial Statistician will be fully blind until the first version of the SAP is approved by the Data Monitoring Committee (DMC).

After the first version of the SAP is approved by the DMC, the Junior Trial Statistician will become unblinded and access participant level data by arm. The Junior Statistician will then have access to the adherence data and be able to monitor and inform the DMC of the trial adherence of the participants. They will present the closed DMC report to the DMC members.

The Junior Trial Statistician will not take part in any discussion that influences the early stopping of the trial at any TMG, TSC, or DMC meetings.

12.3 **GENERAL PRINCIPLES**

We will report data in line with the Consolidated Standards of Reporting Trials (CONSORT) for multiarm trials showing attrition rates and loss to follow-up. This will include the number of eligible patients, number of patients agreeing to enter the trial, number of patients refusing, then by intervention arm: the number of patients compliant/non-compliant with treatment, the number continuing through the trial, the number withdrawing, the number lost to follow-up and the numbers excluded/analysed at each time point.

Analyses will be carried out using the intention to treat principle: participants will be analysed in the group they are randomised to, and available data from all participants are included, including those who do not complete therapy. Every effort will be made to follow up all participants in all arms for research assessments. For estimates of treatment effects in each comparison, only participants who could have been randomised to either arm (i.e. not contraindicated to either drug and contemporaneously randomised) will be included in that comparison.

Analysis will be conducted in Stata version 17.0 or later.

12.4 **BASELINE CHARACTERISTICS**

No statistical significance tests or confidence intervals will be calculated for the difference between randomised groups on any participant level baseline variables. The randomisation of participants to intervention groups means that any imbalance over all measured and unmeasured baseline characteristics is by definition due to chance.

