13.1.2 ECONOMIC EVALUATION ANALYSIS

Costs will be estimated from the perspective of the NHS and Personal Social Services³⁸, by attaching published unit costs for the most recent price year (example sources include Jones et al 2024, NHS England 2021/22, NHSBSA 2022/23)³⁹⁻⁴¹. Wider resource impacts on the participants, in terms of employment and out of pocket costs, will be analysed separately. The utility score from the EQ-5D-5L will be used to estimate QALYs for the trial period using linear interpolation and area-under-the-curve analysis with and without adjusting for baseline differences⁴². We will value the EQ-5D-5L in our primary analysis in line with NICE recommendations at the time of analysis.

The economic evaluation will estimate the mean incremental cost and mean incremental QALYs of the comparator drugs at 6 and 12 months (given the timeframe costs and benefits will not be discounted). A regression-based approach (for instance seemingly unrelated regression equations if assumptions are met⁴³) will be used to estimate the mean incremental cost and effects with and without adjusting for difference in baseline characteristics (EASI score, costs, EQ-5D, duration of disease) and minimisation factors (recruitment centre, severity). In line with the guide to handling missing data in within trial cost-effectiveness analysis⁴⁴, the pattern and nature of the missingness will be explored using descriptive analyses (e.g. amount of missing data by trial group at each time point; missing patterns; association between missingness and baseline variables; and association between missingness and observed outcomes). We will use this analysis to choose an appropriate method to handle any missing data.

Since cost data are likely to be skewed, we will use non-parametric bootstrapping to estimate mean (95% CI) incremental cost and mean (95% CI) incremental QALY. Treatment options will be ranked from least to most costly, any option that is strongly dominated (i.e. options which are inferior in terms of both cost and outcome) will be ruled out before estimating incremental cost effectiveness ratios (ICERs) and/or net monetary benefits as appropriate (NMBs). These will then be examined for extended dominance, where treatment options with a higher ICER than options that follow, will be removed and ICERs/NMB re-estimated. Bootstrapping will also be used to explore the level of uncertainty associated with the decision to adopt a treatment through the estimation of cost-

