17.1 STATISTICAL CONSIDERATIONS

Each additional arm will be considered as a new parallel-group comparison against the nominated standard of care (currently ciclosporin). The advantages of considering these new comparisons in a future platform are multiple:

- a. statistical efficiency from the use of a single control group
- b. operational efficiency from adding a new arm into an existing protocol and database
- c. cost efficiency compared to setting up an independent parallel-group trial

Design considerations for MAMS trials include controlling the type 1 error rate. If the additional trial arms are different, the emphasis should be on controlling the pairwise error rate and powering each research arm separately, as though an independent trial⁴⁷. Therefore, there are no additional considerations for the three-arm trial at this stage, which already has a conservative pairwise adjustment of 0.025. If new arms are added late during the course of this study, there will be little overlap in shared control arm information, which will further reduce the correlation between the pairwise comparisons, and the need to change the type I error for the current arms. However, the timing of new arms will impact on the length of the study required to randomise a concurrent control group with the same eligibility criteria, and we may adjust the randomisation ratio to produce results from each comparison at a similar time.

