1.1.4 RATIONALE FOR 6 MONTH SWITCH OPTION FROM CICLOSPORIN (DUPILUMAB)

For those participants on ciclosporin who do not meet response criteria to continue at 6 months they can switch to dupilumab. Dupilumab was chosen as the switch option to most closely mirror clinical practice (in line with NICE TA534).

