1.1.4 RATIONALE FOR 6 MONTH SWITCH OPTION FROM METHOTREXATE (DUPILUMAB)

For those participants on methotrexate who do not meet response criteria to continue at 6 months they can switch to dupilumab. Dupilumab was chosen as the switch option to most closely mirror clinical practice (in line with NICE TA534).

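### Month-9/12 and 12-month results are worded as drug versus ciclosporin, but after the month-6 switch they compare starting strategies, and the control arm contains dupilumab

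*Protocol*

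**What the plan says.** **What is asked.** Objective 1 in section 3.2 is to "Determine the effectiveness of systemic treatments compared with standard of care over 12 months". Objective 4 is to "Determine cost-effectiveness of systemic treatments compared with standard of care over 12 months". Objectives 2, 3 and 6 set the same comparison over 12 months for symptoms and quality of life, for safety and tolerability, and for adverse events of special interest (AESIs).

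**What standard of care means.** The primary objective in section 3.1 makes it the control drug: "compared with the control systemic treatment ('standard of care') over 6 months". Section 17.1 names ciclosporin as the current one.

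**What happens at month 6.** Appendix 1 (1.1.4): "For those participants on ciclosporin who do not meet response criteria to continue at 6 months they can switch to dupilumab". Appendix 2 (1.1.4): "For those participants on methotrexate who do not meet response criteria to continue at 6 months they can switch to dupilumab". Appendices 3 and 4 (1.1.4) send dupilumab and abrocitinib non-responders to methotrexate. Under section 5.3.3, a non-responder for whom the switch is not possible is withdrawn.

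**How the data are analysed.** Section 12.3: "participants will be analysed in the group they are randomised to, and available data from all participants are included". Section 4.2 lists month-9 and month-12 outcomes. Section 12.5.2 gives continuous outcomes the primary model and binary outcomes logistic mixed models, and mentions no rule or term for the switch. Section 13.1.2 will estimate "mean incremental cost and mean incremental QALYs of the comparator drugs at 6 and 12 months".

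**The concern.** Put together, these statements do not describe one quantity. The objectives and section 13.1.2 speak of a drug compared with ciclosporin over a year. The analysis compares groups in which, from month 6, many participants may no longer be on the drug that names their arm. For dupilumab, the month-12 contrast is dupilumab (then methotrexate on non-response) against ciclosporin (then dupilumab on non-response).

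Followed as written, a control participant who fails ciclosporin and then clears on dupilumab counts as a 12-month success for ciclosporin. The cost of that dupilumab is charged to the ciclosporin arm. Safety has the same difficulty: ocular surface disease is an AESI (section 10.2), and Appendix 3 (1.2.1.1) describes ocular reactions as commonly associated with dupilumab, so such events in switched controls would be counted under ciclosporin. A reader who takes the stated objective at face value would read a strategy result as a drug result.

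**Working it through.** **1. The plan's own figure, and what it covers.** Section 12.1: difference 6.6, SD 13.6, two-sided alpha 0.025, power 90%, 20% loss.

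- n = 2 × (2.2414 + 1.2816)² × (13.6/6.6)² = 2 × 12.411 × 4.246 = 105.4, so 106 analysed per arm. 106/0.8 = 132.5, so 133.
- A t-based check gives 90.1% power at 107 per arm, and 107/0.8 = 133.75, so 134, as stated.

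The figure reproduces. It concerns month 6 only; the protocol states no sample size or power for month 9 or 12.

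**2. What each arm contains after month 6.**

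| Randomised to | Months 0-6 | Months 7-12, responders | Months 7-12, non-responders who switch |
|---|---|---|---|
| Ciclosporin (control) | ciclosporin | ciclosporin | dupilumab |
| Methotrexate | methotrexate | methotrexate | dupilumab |
| Dupilumab | dupilumab | dupilumab | methotrexate |
| Abrocitinib | abrocitinib | abrocitinib | methotrexate |

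Every month-9/12 contrast with control therefore mixes drugs on both sides. In the dupilumab contrast the control arm contains the drug being tested.

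**3. How much dupilumab the control arm could carry.** The switch share f is not in the protocol. The only ciclosporin response figure (section 1.4) is 80% EASI50 at 24 weeks in an earlier trial, which leaves 20% failing EASI50. The trial's rule also requires a DLQI gain of at least 4 points, so f could be higher. Assumed range: 20-40%.

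- Control arm: f × 6 months = 0.2 × 6 = 1.2 to 0.4 × 6 = 2.4 dupilumab-months per person, or 10-20% of the 12 months.
- Dupilumab arm, with response p of 61-69% (EASI50 at 16 weeks, section 1.4): 12p + 6(1 − p). For p = 0.61 this is 7.32 + 2.34 = 9.66; for p = 0.69 it is 8.28 + 1.86 = 10.14.
- Ratio of control to dupilumab arm: 1.2/10.14 = 0.12 to 2.4/9.66 = 0.25.

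This assumes that EASI50 alone stands for response in the dupilumab arm, that every non-responder switches, and that nobody stops early.

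**4. EASI, as illustration only.** Suppose the drug-only difference at month 12 were 6.6, switched controls gained all of it, and the dupilumab arm were unchanged. The as-randomised difference would be 6.6 × (1 − f): 5.28 at f = 0.2 and 3.96 at f = 0.4. None of these three conditions comes from the documents.

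**The case against.** The strongest reply is that the design is deliberate and disclosed. Section 2 says that the switch mirrors real-world practice, and Appendix 1 ties the move to dupilumab to NICE guidance, so a control arm that sends its failures to dupilumab resembles the care pathway. Section 1.2 and objective 5 raise the pathway question openly, section 12.9 plans Q-learning for it, and section 13.1 estimates costs and QALYs by arm. The comparison by randomised arm is a proper randomised comparison of starting strategies, and a drug-level result already exists at month 6. Details of switch handling can be left to the SAP and the health economics analysis plan.

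Most of this stands, and it limits the point to what the 12-month results are said to estimate. It does not remove it. Objective 5 and Q-learning ask which pathway is best; they do not redefine objectives 1, 2 and 4. The objective wording, the meaning of standard of care, the as-randomised rule and the drug label in section 13.1.2 are fixed in the protocol, so an SAP that followed them would inherit the mismatch.

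Four stronger readings are tempting, and the documents support none of them:

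- **That the 12-month contrasts are biased or invalid.** They are valid for strategies. Calling the control arm's dupilumab cost an error presumes a comparison with non-responders kept on ciclosporin, which the protocol never sets as its counterfactual.
- **That month-12 power falls by a known amount.** No month-12 power is stated, the switch share is unknown, and a switch that helps the worst participants would also change the SD. No power figure should be quoted.
- **That dupilumab's advantage shrinks by a known amount.** The cited 80% and 61-69% come from different trials and time points and, taken together, would not even favour dupilumab.
- **That the standard-of-care decision (17.2) or the long-term model (13.2) will be distorted.** The decision factors are in a figure that is not shown, and the model's data sources are left to later review.

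**Conclusion.** The point holds as a mismatch between the stated objectives and what the planned analysis estimates. Objectives 1, 2 and 4, the 12-month parts of 3 and 6, and section 13.1.2 describe drugs against ciclosporin; the as-randomised month-9/12 results compare starting strategies that include a pre-defined switch. The month-6 primary result and the 6-month economic result concern the period before the switch and are not affected.

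The size depends on an unstated switch share. At an assumed 20-40% of controls, the control arm averages 1.2-2.4 dupilumab-months per person, which is 12-25% of the use in the dupilumab arm. That is enough to matter for how 12-month costs, adverse events and response rates are read. The EASI dilution is illustrative only. The correction is worth making because it is cheap and concerns results meant for guideline and commissioning readers, but it does not threaten the trial's main conclusion.

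**What to change.** - **Reword** objectives 1, 2 and 4, the 12-month parts of 3 and 6, and section 13.1.2, so that month-9/12 contrasts and 12-month ICERs compare starting strategies including the month-6 switch. Name month 6 as the drug-versus-drug result.
- **Add one supplementary month-9/12 analysis** of the binary outcomes (EASI50/75/90/100, EASI of 7 or less, vIGA-AD and PtGA clear or almost clear, DLQI of 5 or less). It counts participants switched or withdrawn for non-response at month 6 as not achieving the outcome on the randomised drug.
- **Tabulate** 12-month adverse events and AESIs by drug taken at onset as well as by randomised arm.
- **Keep exploratory** any continuous analysis that sets post-switch values to missing. Few non-responders would remain on the randomised drug, so it is largely extrapolation. Switching also depends on DLQI, so the analysis should condition on month-6 EASI and DLQI.

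The cost is wording in the protocol, SAP and health economics analysis plan, plus a little extra analysis of data already planned for collection. The supplementary analysis has its own limit: it treats every switch for non-response as failure, so it answers a narrower question than the strategy comparison. No change to the clinical switch rule is implied.
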